Assessment and prediction of the effectiveness of anti-IL-5/IL5R inhibitors in a real-world setting: a two-step study

[name] [name]

[name] PhD

CIUSSS du Nord de l'île de Montréal, Hôpital du Sacré-Cœur de Montréal

Université de Montréal

NCT06239441

Scientific rationale

Asthma is a chronic respiratory disease affecting up to 8.4% of Canadians (1). While the majority of asthmatics are controlled with a low dose of inhaled corticosteroids (ICS), there are still approximately 10% of asthmatics who remain uncontrolled despite using high doses of an ICS with additional controllers. These patients are defined as severe asthmatics (2).

Over the past decade, it has become obvious that asthma is a heterogeneous disease that is composed of several phenotypes. The identification of those phenotypes has been associated with the development of biological therapies that specifically target antibodies, cytokines, and their receptors, such as immunoglobulin E, interleukin (IL) -5, and IL-5 receptor or IL-13/IL-4 receptor in the treatment of severe cases of asthma. Interleukin (IL)-5 plays a central role for eosinophil recruitment, activation, and survival. IL-5 and its receptor (IL-5R) have been targeted for developing antagonists against this cytokine or its receptor in the improvement of asthma control. There are three drugs targeting IL-5 or its receptor that have been developed to treat severe eosinophilic asthma: mepolizumab (NucalaTM), reslizumab (CinqairTM), and benralizumab (FasenraTM). Mepolizumab a humanized monoclonal anti-IL-5 (IgG1) antibody was the first IL-5 antagonist to be commercialized in 2016 followed by reslizumab a humanized anti-IL-5 (IgG4/k) antibody. Benralizumab a humanized monoclonal antibody against interleukin 5 receptor α (IgG1 κ) was commercialized in 2018 in the province of Quebec.

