The majority of patients receiving anti-IL-5/IL5R inhibitors will have at least a 50% decrease in their asthma exacerbations rate in a tertiary clinic specialized in the field of severe asthma.

The level of blood and sputum eosinophils will be the main response predictor to anti-IL-5/IL5R inhibitors in a tertiary clinic specialized in the field of asthma whereas the rate of exacerbation in the year prior to the initiation of anti-IL-5/IL5R inhibitors will be the main predictor of asthma exacerbations in a non-selected population of severe asthmatics in Quebec.

Primary Objectives

1. To assess and compare the response* to treatment before and after the initiation of anti-IL-5/IL5R inhibitors in patients followed in a tertiary asthma clinic from the Province of Quebec and in a non-selected population of asthmatic subjects covered by the *Régie de l'Assurance Maladie du Québec*'s (RAMQ) public drug insurance plan or by a private drug insurance.
2. To assess the clinical response predictors to anti-IL-5/IL5R inhibitors in a cohort of severe asthmatics followed in tertiary care as well as in a non-selected population of asthmatic subjects covered by the RAMQ's public drug insurance plan *or by a private drug insurance*.

* Response to treatment will be defined by a reduction of asthma exacerbations of at least 50% *and* or a 50% or higher reduction of the OCS doses in steroid dependent patient compared to the year prior to treatment initiation.

Secondary objectives:

1. To assess the mean reduction of exacerbation in both cohorts.
2. To assess the adherence and persistence to treatment with anti-IL-5/IL5R inhibitors and ICS after treatment initiation with anti-IL-5/IL5R inhibitors..

Study populations.

A) A Tertiary asthma clinic cohort of patients 18 years and older who are followed at the outpatient asthma clinic of Sacre-Cœur Hospital and who have been treated with anti-IL-5/IL5R inhibitors between January 2016 and June 2020 and are included in the reMed database;

We will ensure that those patients had severe eosinophilic asthma inadequately controlled on high dose ICS plus additional controlled therapy and had a blood eosinophil count of 150 cells/ μ L on initiation or 300 cells/ μ L in the past 12 months and had either 2 or more significant asthma exacerbations in the past 12 months or were treated with daily oral steroids

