A retrospective pre-post anti-IL-5/IL5R inhibitors treatment cohort study using the RESP database and the hospital charts including patients with severe asthma followed at the *Hôpital du Sacré-Coeur de Montréal* (Tertiary asthma clinic cohort).

Another retrospective pre-post anti-IL-5/IL5R inhibitors treatment cohort selected from the Quebec health administrative databases and reMed database (Population-based cohort).

Cohort entry will be defined as the first prescription of anti-IL-5/IL5R inhibitors filled on or after January 1, 2016 for both cohorts.

Outcomes

Objective 1, primary outcome: Response to anti-IL-5/IL5R inhibitors, defined by a reduction of asthma exacerbations of at least 50% and a 50% or higher reduction of the OCS doses in steroid dependent patients in the year following the initiation of anti-IL-5/IL5R inhibitors compared to the year prior to treatment initiation, in the tertiary asthma clinic cohort and in the population-based cohort.

Objective 1, secondary outcomes: Exacerbation rates and OCS doses (for steroid-dependent patients) in the year preceding and following initiation of anti-IL-5/IL5R inhibitors in the tertiary asthma clinic cohort and in the population-based cohort.

Objective 2: Response to anti-IL-5/IL5R inhibitors in the tertiary asthma clinic cohort and in the population-based cohort in the year following initiation of anti-IL-5/IL5R inhibitors.

Potential Predictors

Potential clinical response predictors to anti-IL-5/IL5R inhibitors in the Tertiary asthma clinic cohort are: age, sex, atopy, body mass index, smoking habits, percent predicted FEV₁, asthma treatment prescribed, blood eosinophil count, and sputum eosinophil count at cohort entry.

Potential clinical response predictors to anti-IL-5/IL5R inhibitors in the Quebec population (Population-based cohort) are: age, sex, type of asthma treatment filled in the year before treatment initiation with anti-IL-5/IL5R inhibitors adherence to ICS in the year before and after treatment initiation with anti-IL-5/IL5R inhibitors, exacerbation rate in the year before treatment initiation with anti-IL-5/IL5R inhibitors, and socio economic status (welfare recipients).

Source of data

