The reMed database contains data on medications dispensed in community pharmacies to a sample of patients with private drug insurance. The reMed contains the HCIN, the private insurance policy number (PIPN), the type of insurance plan (co-payment, annual premium, and so on), the name, dose formulation and quantity of the medication dispensed, the date the medication was dispensed, the pharmacy & the prescriber's encoded identifier, the cost of medications, and the amount reimbursed by the insurer. The drug related variables recorded in reMed are almost identical to the variables recorded in the RAMQ Prescription Medications file. The HCIN allows the linkage of the reMed to the RAMQ and MED-ECHO databases.

Methods

After having obtained the authorization from the research ethics committee of the CIUSSS du Nord-de-l'île-de-Montréal and from the director of Professional Services, all the charts of patients who received anti-IL-5/IL5R inhibitors at the tertiary asthma clinic of *the Hôpital du Sacré-Coeur de Montréal* will be reviewed.

A response to treatment will be defined by a 50% reduction in the number of asthma exacerbations in the year following the initiation of anti-IL-5/IL5R inhibitors compared to the year preceding the initiation of the treatment or a 50% decrease in the OCS doses for steroid dependent patients.

A functional response to treatment will also be assessed in the Tertiary asthma clinic cohort. An improvement of FEV₁ of 12 % and ≥ 200 ml will be considered as clinically significant.

Asthma exacerbations will be defined by a short treatment with systemic corticosteroids (less than 14 days), visit to the emergency department or hospitalization related to asthma. If two markers of an asthma exacerbation occurred with 14 days, they will be counted as only one exacerbation. This definition will be applied in the Tertiary asthma clinic cohort and the population-based cohort.

The potential predictors of response to treatment will be collected in the Quebec registry in respiratory health (RESP) database and or the medical charts: age (continuous), sex (women/men), atopy (atopic/non atopic), body mass index (continuous), smoking habits (current or ex/never smokers)(never/ever/current), percent predicted FEV₁, asthma treatment (dose of ICS, dose of OCS if any), exacerbation rate in the year preceding treatment initiation, blood eosinophil count, and sputum eosinophil count.

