We shall require the authorization from *the Commission d'accès à l'information du Québec* to obtain the RAMQ and MED-ECHO data on healthcare utilization and medication for all subjects who have been diagnosed with asthma and who have been receiving anti-IL-5/IL5R inhibitors between January 2016 and June 2020; for example, subjects included in the tertiary asthma clinic cohort and the population-based cohort.

We will require from the RAMQ and MED-ECHO, the data on visits to the physicians, visits to the emergency departments, and hospitalizations for asthma and any other medical issues as well as the use of medication of all patients who have been diagnosed with asthma as defined by a validated operational definition(12) – 2 ambulatory visits for asthma or an hospitalization for asthma within the past 2 years a – in the year preceding the prescription of anti-IL-5/IL5R inhibitors and who have been receiving anti-IL-5/IL5R inhibitors from January 2016 to June 2020 in the Province of Quebec. We will request the data from January 2014 to June 2021.

Statistical analysis

We will estimate the proportion and confidence interval of patients' responder to anti-IL-5/IL5R inhibitors in the Tertiary asthma clinic cohort and the population-based cohort.

A logistic regression model will be used to identify the response predictors to anti-IL-5/IL5R inhibitors. Variable selection will be made with the Lasso selection procedure (13).

We will perform a Poisson regression model to compare the exacerbation rate in the year before and after the treatment initiation with anti-IL-5/IL5R inhibitors in the tertiary asthma clinic cohort and the population-based cohort. We will include all patients who received anti-IL-5/IL5R inhibitors in the analysis. The duration of follow-up will be taken into account using an offset in the Poisson regression model.

We will perform a linear regression model to compare the OCS doses in the year before and after the treatment initiation with anti-IL-5/IL5R inhibitors in the tertiary asthma clinic cohort and the population-based cohort.

Sample size and statistical power

To fulfill the primary objective

With 60 patients in the Tertiary asthma clinic cohort and an expected response rate of 50% we will have the power to identify 6 predictors (14). With 570 patients in the population-based cohort and an expected response rate of 50% we will have the power to identify more than 50 predictors (14).

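### A patient who fails anti-IL-5/IL5R treatment and is rescued within the year, most clearly by new daily OCS, can be scored as a responder

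*Combined protocol and SAP*

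**What the plan says.** Response is defined in three places.

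- **Methods:** "A response to treatment will be defined by a 50% reduction in the number of asthma exacerbations in the year following the initiation", compared with the preceding year, "or a 50% decrease in the OCS doses for steroid dependent patients".
- **Outcomes (Objective 1, primary):** "a reduction of asthma exacerbations of at least 50% and a 50% or higher reduction of the OCS doses in steroid dependent patients".
- **Primary Objectives (footnote):** the same two limbs, joined by *and or*.

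The year runs from treatment initiation, and cohort entry is the first fill (Study design). Nothing ties it to time on the drug. Exacerbations are "defined by a short treatment with systemic corticosteroids (less than 14 days), visit to the emergency department or hospitalization" for asthma (Methods).

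Under Statistical analysis, the responder proportion is estimated with a confidence interval, and response is the outcome of the logistic predictor model. Two sentences on handling patients, "We will include all patients who received anti-IL-5/IL5R inhibitors in the analysis" and "The duration of follow-up will be taken into account using an offset in the Poisson regression model", belong to the paragraph on the Poisson rate model. The binary response has no counterpart.

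A secondary objective is "To assess the adherence and persistence to treatment with anti-IL-5/IL5R inhibitors and ICS after treatment initiation" with these drugs. It is not linked to the response definition. No section says how to score a patient who stops, changes biologic class or starts daily OCS.

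**The concern.** The outcome is labelled response to anti-IL-5/IL5R inhibitors, but it is read from everything that happens in a calendar year. If the drug fails and something else controls the asthma for the rest of that year, the improvement is credited to the drug under study.

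For OCS the problem is built into the definitions. A failing patient moved from repeated short courses to continuous OCS stops generating countable steroid courses, whether or not the OCS helps. If that patient was not steroid dependent before, no dose criterion clearly applies.

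Two results are exposed: the responder proportion, and the predictor model, where some failures would be coded as successes. Compared with scoring rescue as failure, the error can only raise the proportion.

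**Working it through.** The plan gives no figure for rescue, switching or new OCS, so there is none to reproduce. The planning values that bear on the point are the expected response rate of 50% and the cohort sizes of 60 and 570 (Sample size and statistical power).

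**1. New OCS under the definitions as written.** As an illustration, take a patient who was not steroid dependent and had 4 short courses in the pre-year.

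- Flares continue and are treated with short courses: 4 against 4, no reduction, non-responder.
- One short course, then continuous OCS from month 3 with no emergency visit or admission: 1 against 4, a 75% reduction, so the exacerbation limb is met.
- The same, plus one separate emergency visit and one separate admission: 3 against 4, a 25% reduction, limb not met.

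The second patient's score depends on the wording used and on when steroid dependence is judged, which is not stated:

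| Response definition | Dependence fixed at entry | Dependence arising later counts |
|---|---|---|
| Outcomes (*and*) | responder | non-responder |
| Methods (*or*) | responder | responder |
| Primary Objectives (*and or*) | responder | undetermined |

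**2. When rescue is enough to meet the 50% rule.** Suppose the exacerbation rate is unchanged until rescue at month t and is multiplied by f afterwards. The expected post/pre ratio is t/12 + f(1 − t/12). Setting it at or below 0.5 gives t ≤ 12(0.5 − f)/(1 − f):

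- f = 0: month 6 or earlier
- f = 0.25: month 4 or earlier
- f = 0.5: 12 × 0/0.5 = 0, so never after entry

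**3. Allowing for chance.** Take a pre-year count c of 2, 3, 4 or 6 and a Poisson post-year count with mean c[t/12 + f(1 − t/12)]. The probability that the post count is at most c/2 ranges over c as follows:

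| Rescue at | f = 0 | f = 0.25 | f = 0.5 |
|---|---|---|---|
| month 3 | 0.83-0.93 | 0.62-0.78 | 0.44-0.64 |
| month 6 | 0.56-0.74 | 0.44-0.64 | 0.34-0.56 |
| month 9 | 0.34-0.56 | 0.28-0.52 | 0.23-0.48 |
| no rescue | 0.15-0.41 | 0.15-0.41 | 0.15-0.41 |

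One half is a middling assumption for the share of rescued patients who meet the rule.

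**4. Effect on the responder proportion.** Excess = share rescued × (share of them meeting the rule − share that would have met it without rescue). The shares are assumptions: 5-15% rescued, 0.50 meeting the rule, 0.15-0.41 meeting it anyway.

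- Low: 0.05 × (0.50 − 0.41) = 0.0045, about 0.5 points
- High: 0.15 × (0.50 − 0.15) = 0.0525, about 5 points

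In patients, this is 0.3 to 3.2 of 60 and 2.6 to 29.9 of 570.

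**5. Against the precision.** The 95% half-width at 50% is 1.96 × √(0.25/n): 12.7 points for n = 60 and 4.1 points for n = 570. Only the top of the range exceeds the half-width in the population-based cohort. In the clinic cohort the excess stays well inside it.

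**The case against.** The strongest reply is that counting everything in a fixed year after initiation is a legitimate treatment-policy comparison for a real-world study. That stands for biologic switching. The claims fields listed under Source of data give no reason for a switch, so treating every switch as failure in the primary analysis would also catch changes made for tolerability or coverage. It stands less well for new OCS, where the exacerbation definition itself removes events, and the plan does not say it chose this comparison.

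A reader might also infer several stronger things that the documents do not support:

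- *Rescued failures are always scored as responders.* They must still show a 50% lower count over the whole year, including events before rescue. Late or weak rescue often fails that test.
- *Switching is documented in these patients.* The phrase "IL-5 receptor or IL-13/IL-4 receptor in the treatment of severe cases of asthma" is general background in the Scientific rationale. Omalizumab is listed only as a predictor, which Outcomes frames as treatment filled before initiation. That some patients remain uncontrolled on these drugs is said without mention of switching.
- *The all-patients sentence governs the responder proportion.* It sits in the Poisson paragraph.
- *The bias is the full 5-15% × 0.5 = 2.5-7.5 points.* That counts patients who would have met the rule anyway.
- *The error decides whether a majority respond.* That hypothesis concerns the tertiary clinic only, where the excess is small beside the confidence interval. The 50% is a planning value, and no test against it is specified.
- *New OCS is never examined.* The linear model under Statistical analysis compares OCS doses without naming a restriction, although Outcomes limits the dose outcome to steroid-dependent patients. Either way, that model does not alter who is called a responder.

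**Conclusion.** The gap is real. With the response rule as written, a patient who was not steroid dependent at entry and moves to daily OCS after treatment failure can be classified as a responder to the drug that failed. If dependence is judged at entry, all three wordings allow this. If it is judged later, they disagree. This goes beyond missing detail, because following the text can misclassify patients. An effective early switch of biologic class can have a similar effect, but how to treat it is a choice of estimand that the plan should state.

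The size is unknown. Under the assumptions shown, the excess is about 0.5-5 percentage points. It rests on an assumed rescue rate of 5-15%, an assumed half meeting the rule, and Poisson counts with a constant underlying rate. Regression to the mean after entry on a high count would raise the no-rescue share and tend to shrink the excess.

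**What to change.** 1. State that steroid dependence is determined at cohort entry. Reconcile the response definitions in Primary Objectives, Outcomes and Methods into one. Score a patient who starts maintenance OCS not present before entry as a non-responder, in both the responder proportion and the predictor model. The sponsor should set the duration that defines maintenance use.
2. State that the primary analysis counts the full year regardless of biologic switching. Add a sensitivity analysis of the proportion and the predictor model in which a fill of another biologic class within the year is scored as non-response.

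This concerns outcome classification only and affects no treatment decision.

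The cost is protocol wording and two flags from dispensing data already requested. Drug name, quantity and date are listed for RAMQ and reMed. Duration is listed explicitly only for RAMQ, so in reMed it may have to be derived from quantities and refill dates. The data request to June 2021 covers the full year for entrants up to June 2020. The downsides are a slightly lower response proportion and some misclassification, because claims do not give the reason for a switch or for OCS. Charts in the clinic cohort may record it, but the plan does not list it as an item to collect.

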The Quebec Registry in Respiratory Health (RESP) is a database originally built in 2010 by [name]. This registry aims to store clinical and functional data in subjects with asthma and COPD followed at the *Hôpital du Sacré-Coeur de Montréal* or at the *Centre Hospitalier Universitaire de Sherbrooke*. The patients included in the database have also consented to have their clinical data matched to the *Régie de l'assurance médicale du Québec* (RAMQ) and *Maintenance et exploitation des données pour l'étude de la clientèle hospitalière* (MED-ECHO) administrative databases and the reMed database on medications for patients with private health insurance plans which enables access to data on medical services, hospitalisations and medications dispensed by pharmacies. This databases allows us to collect the following variables: age, sex, area of residence (rural or urban), treatment (if insured with the RAMQ), comorbidities, visits to the physician for asthma and all causes, visits to the emergency for asthma and any other medical issues, and hospitalization for asthma and any other medical issues.

This database allows us to assess the adherence to inhaled corticosteroids (ICS) by calculating the proportion of days covered (PDC) (11), a measure of adherence based on prescription claims data. The PDC is defined as the sum of the duration of all prescriptions of ICS filled over one year, divided by 365 days, expressed in percentages. The PDC will be estimated using prescription refill

data obtained from the RAMQ and reMed databases in the year preceding and following cohort entry.

Potential response predictors to treatment will also be collected in the RAMQ and reMed databases: age (continuous), sex (women/ men), type of asthma treatment (ICS, long-acting beta 2 agonists (LABA), Long-acting muscarinic antagonists (LAMA), Leukotriene-receptor antagonist (LTRA), omalizumab, or OCS if any), adherence to asthma treatment before and after cohort entry, comorbidities as measured by the Charlson score before and after cohort entry, exacerbation rate in the year preceding cohort entry, and area of residence (rural or urban) at cohort entry.

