With 60 patients in the tertiary asthma clinic cohort, an expected rate of 1.48 exacerbations per year per patient (3), and an alpha error of 5%, we will have a power of 80% to show a reduction of 50% in the rate of exacerbation (1 year post- anti-IL-5/IL5R inhibitors versus 1 year pre- anti-IL-5/IL5R inhibitors). With 570 patients in the population-based cohort and the same assumptions, we will have more than 90% power to show a reduction of 50% in the rate of exacerbation (1 year post- anti-IL-5/IL5R inhibitors versus 1 year pre- anti-IL-5/IL5R inhibitors).

Limitations

Fifty eight percent of Quebecers are covered by a private drug insurance. With reMed, we will be able to obtain this data for only a small sample of patients with a private drug insurance plan.

Perspective:

Up to date, the main prognostic factor identified in subjects treated with anti-IL5 is the level of eosinophilic inflammation. However, this factor has been identified in subjects enrolled in clinical trials. It is unknown whether, smoking, co-morbidities or adherence to ICS affects the response to anti-IL-5/IL5R inhibitors. This study will be the first to answer this question in both a selected population followed in a tertiary asthma clinic and in a large population from Quebec.

Schedule of Activities

Study Procedures	Estimated Date
Ethic committee submission	November 2020
Submission to the Commission d'accès à l'information du Québec/RAMQ	December 2020
Clinical Data collection from RESP and hospital charts.	December 2020
First data analysis for clinical data And RAMQ data reception	March 2021
Submission of an abstract to the ATS	November 2021
Data Analysis	September 2021
Report and article writing	October 2021

References

1. Canada Go. Fast facts about asthma: Data compiled from the 2011 Survey on Living with Chronic Diseases in Canada

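### The ICS adherence measure is called proportion of days covered, but its formula adds up days supplied over a fixed 365, so it does not count days covered

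*Combined protocol and SAP*

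**What the plan says.** The Methods section proposes to assess ICS adherence by "calculating the proportion of days covered (PDC) (11), a measure of adherence based on prescription claims data". It then gives the rule: "The PDC is defined as the sum of the duration of all prescriptions of ICS filled over one year, divided by 365 days", expressed as a percentage. The inputs are refill "data obtained from the RAMQ and reMed databases in the year preceding and following cohort entry".

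The measure has two uses:

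- Secondary objective 2 is "To assess the adherence and persistence to treatment with anti-IL-5/IL5R inhibitors and ICS after treatment initiation" of the biologic.
- Under Potential Predictors, the list for the population-based cohort includes "adherence to ICS in the year before and after treatment initiation with anti-IL-5/IL5R inhibitors". The Methods list of RAMQ and reMed predictors also includes adherence before and after cohort entry.

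The Perspective section gives the motivation: "It is unknown whether, smoking, co-morbidities or adherence to ICS affects the response to anti-IL-5/IL5R inhibitors".

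The protocol states no cap at 100%, no rule for overlapping fills or for two ICS products held on the same day, no truncation of supply at the end of the window, no treatment of supply already in hand at its start, and no denominator other than 365. Unequal follow-up is addressed only for exacerbation rates, under Statistical analysis: "The duration of follow-up will be taken into account using an offset in the Poisson regression model".

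**The concern.** A day is either covered or not, so a proportion of days covered lies between 0% and 100%. A sum of supply durations has no such limit. The name and the formula therefore describe different quantities, and a programmer following the text would compute the second.

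The two diverge in four situations: overlapping supply (early refills, a switch with stock left over, or two ICS products held together), supply filled late in the year and used after it, supply filled before the year and used within it, and a year that is only partly observed. The first two raise the score; the last two lower it.

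At stake are the adherence figures reported for secondary objective 2 and the meaning of ICS adherence as a candidate in the population-based predictor model. The Perspective section presents that as an open question the study will be first to answer, so the variable should measure what its name says.

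**Working it through.** The documents report no adherence value, so there is no figure to reproduce. The check applies the stated formula to constructed fill histories and compares it with a count of covered days.

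**Formulas**

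- Protocol: sum of fill durations / 365.
- Comparator: distinct days in the window with at least one ICS on hand (same-product overlap carried forward, supply cut at the window end) / days observed.

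**Inputs.** The protocol formula comes from Methods. The fill histories are assumptions that show only how the formula behaves. Day 0 is the start of the window, with no carry-in unless stated.

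| Fill history | Protocol formula | Days covered |
|---|---|---|
| 13 on-time 30-day fills | 390/365 = 106.8% | 100% |
| 30-day fills every 25 days (15 fills) | 450/365 = 123.3% | 100% |
| Five on-time 90-day fills, the last on day 360 | 450/365 = 123.3% | 100% |
| 90-day fills on days 0, 180 and 360 | 270/365 = 74.0% | (90+90+5)/365 = 50.7% |
| Two ICS products together, 12 × 30 days each | 720/365 = 197.3% | 360/365 = 98.6% |
| Two ICS products together every second month, 6 × 30 days each | 360/365 = 98.6% | 180/365 = 49.3% |

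A cap at 100% would repair the first three rows. It would not touch the fourth or the sixth, where the score is wrong but below 100%.

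**Carry-in.** Suppose 30 days of supply remain at day 0, and 90-day fills follow on days 30, 120, 210 and 300. Every day is covered. The formula gives 4 × 90 / 365 = 360/365 = 98.6%: it drops the 30 days carried in and adds 25 days that run past the end (300 + 90 − 365 = 25). The two boundary errors work in opposite directions and here nearly cancel.

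**Part-year observation.** A fully adherent patient whose fills cover exactly the observed days scores:

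- 90 days: 90/365 = 24.7%
- 180 days: 180/365 = 49.3%
- 182 days: 182/365 = 49.9%, about 50%
- 270 days: 270/365 = 74.0%

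The correct value is 100% in each case.

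**Does the data request itself cut years short?** Entry runs from January 2016 to June 2020, and data are requested from January 2014 to June 2021. From 30 June 2020 to 30 June 2021 is 365 days; from 1 January 2014 to 1 January 2016 is 730 days. Every entrant has a full calendar year on each side. Only death, or a gap in public or private drug coverage, can shorten observation. The Source of data section says that RAMQ holds date of death and drug-plan coverage dates; the formula uses neither.

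**The case against.** The strongest reply is that the sentence is shorthand. It names a recognised measure and cites a reference on standard adherence definitions, which may contain the overlap and capping rules. That reference could not be consulted. Even so, the protocol does not defer to it: it writes out an explicit numerator and denominator, and those produce wrong values.

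Other parts of the reply stand and limit the point:

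- **Concurrent ICS.** A reader might infer that double counting is widespread because these patients take high-dose ICS plus further controllers, so that the measure tracks treatment intensity. The documents do not support this. The other asthma treatments listed in Methods (LABA, LAMA, LTRA, omalizumab, oral corticosteroids) are not a second ICS, and nothing says how many patients hold two ICS products.
- **Before/after comparison.** A reader might infer that a planned comparison of adherence between the two years is biased. The measure is computed in both years, but Statistical analysis plans before/after comparisons only for exacerbation rates and oral corticosteroid doses.
- **Short follow-up.** The data window shortens no one's year, and the number of patients who die or lose coverage is not given. The statement "We will include all patients who received anti-IL-5/IL5R inhibitors in the analysis" belongs to the Poisson exacerbation analysis; how part-year patients enter the adherence analysis is not stated.
- **Direction.** Late-year supply inflates the score, while carried-in supply and part-year observation deflate it. Systematic overstatement cannot be concluded.
- **Feasibility in reMed.** The fields listed for reMed include neither prescription duration nor coverage dates, although its drug variables are described as nearly the same as RAMQ's.

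**Conclusion.** The point holds as a mismatch between a named measure and its stated formula. It is a rule that gives wrong values, not merely a missing detail. The individual errors can be large: 123.3% against 100% with early refills, 74.0% against 50.7% with gaps and one late fill, about 50% against 100% with 182 days observed. These rest on assumed fill histories. The frequency of such patterns is not in the documents, so the net bias across patients cannot be sized or signed.

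The reach is limited to secondary objective 2 and to one candidate variable in the population-based predictor model. ICS adherence is not among the predictors listed for the tertiary clinic cohort and is not part of the response definition. Responder proportions, exacerbation rates and oral corticosteroid comparisons are unaffected. The definition should be corrected before the adherence variable is derived; it does not threaten the study's main estimates.

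**What to change.** Replace the definition in Methods with one that counts days:

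- **Numerator:** distinct days in the window with at least one ICS-containing product available. Shift same-product overlap forward, count concurrent products once, state one consistent rule for supply carried in, and truncate supply at the window end.
- **Denominator:** days alive and under drug coverage in that window, so that the maximum is 100%.

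A cap added to the present formula is not enough, as the rows below 100% show.

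For reMed, confirm before programming that prescription duration and coverage dates are available. If coverage dates are not, restrict the adherence analysis to patients with a verifiable full year, or state the limitation.

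The cost is a short protocol edit and slightly more claims programming; for RAMQ, the Source of data section already lists fill date, duration, coverage dates and date of death. Reported adherence will be lower in patients with overlapping fills, and any restriction to verifiable full years will lose some privately insured patients from this analysis.
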